4 SELECTION AND WITHDRAWAL OF SUBJECTS

4.1 Inclusion Criteria

All subjects must fulfil all of following criteria to be included in the study:

- (1) Provision of written informed consent prior to any study related procedures,
- (2) male or female subject (outpatient) legally considered as an adult (age of majority). In Czech Republic the upper limit of age will be 70 years inclusive.
- (3) subject has a diagnosis of acute diarrhoea presumed of infectious origin, defined as:
 - the passage of 3 or more unformed loose or watery stools (rated according to the Bristol scale) per day without associated alarm symptoms*
 - having started within 48 hours before Visit 1 (first study drug intake time).
- (4) subject has, usually, normal bowel habits, (Rome III criteria) **, i.e. at least 3 stools per week and no more than 3 stools per day,
- (5) subject must be willing and able to comply with study restrictions and willing to return to the clinic for the follow up evaluation(s) as specified in the protocol.

*Symptoms considered as alarm symptoms are identified in the exclusion criteria (1)

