5.2 Study Visits

5.2.1 *Visit 1 (Procedures for Enrolment, Day 1)*

A signed and dated informed consent form will be obtained before screening procedures. Evaluations obtained as part of routine medical care and performed during the screening period may be used in place of the study specific evaluations. Subjects will acknowledge and agree to the possible use of this information for the study by giving informed consent.

After informed consent is obtained, at enrolment, subjects will be allocated a subject number. All enrolled subjects must be identifiable throughout the study. The investigator will maintain a list of subject numbers and names to enable records to be found at a later date if required.

Enrolment (Visit 1) will take place within 48 hours after onset of diarrhoea. The following assessments will be performed:

- eligibility check (inclusion/exclusion criteria),
- demographic data (date of birth/age and sex will be collected according to individual country requirements),
- medical and surgical history, including ongoing medical conditions
- history of the current acute diarrhoea episode including:
 - date and time (hours, minutes) of first watery stool,
 - number of stools including number of watery stools and for each 12h period during the last 24 hours,
 - presence of other associated symptoms for the last 24 hours: nausea, vomiting, abdominal pain, anal irritation.
- physical examination,
- vital signs (blood pressure and heart rate in sitting position, respiratory rate, body temperature, body height and weight),
- one faecal sampling for microbiological examination to be collected as soon as possible after inclusion,
- prior and concomitant medications/non-drug therapies (excluding those taken for acute diarrhoea episode) taken within 30 days preceding the enrolment/inclusion visit,
- prior and concomitant medications for acute diarrhoea episode

Following confirmation of eligibility for the study, subjects will be given a randomisation/treatment allocation number and allocated to receive either diosmectite or placebo as specified in Section 6.1.

- collection of AEs,
- study treatment unit will be delivered to the subject according to the randomisation procedure,
- visit Status will be recorded
- start of treatment at the centre: time of first intake of study treatment (data to be recorded in the eCRF).
- the DEB and information for use will be delivered to the subject. Refer to Section 5.2.5 for details to be recorded in DEB

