1.3.2.2 Safety assessments

Adverse Events (AEs)

AEs will be monitored from the time that the subject gives informed consent and throughout the study until 7 days after the end of study treatment

Physical Examination

Physical examinations, including body weight (kg) and body height (cm), will be conducted at Baseline (Visit 1), at Visit 2 and at Visit 3 if applicable. Height will be measured at Baseline only.

Any clinically significant physical examination findings (abnormalities) observed during the study will be reported as AEs. Any physical examination findings

(abnormalities) persisting at the end of the study will be followed by the investigator until resolution or until reaching a clinically stable endpoint.

Vital Signs

Blood pressure (mmHG) and heart rate (bpm) will be recorded after five minutes rest in sitting position at baseline (Visit 1) and each post-baseline visit, as well as body temperature (in °C using an oral/rectal/axillary/auricular/forehead/temporal thermometer).

1.3.2.3 *Other assessments*

Demographic data (date of birth and sex), medical and surgical history, including ongoing medical conditions, prior medications for acute diarrhoea episode as well as other prior medications will be collected at first visit.

A history of current acute diarrhoea episode will also be recorded, including:

- Date and time (hours, minutes) of first unformed loose or watery stool,
- Number of stools including number of unformed loose or watery stools, for each 12h period during the last 24 hours,
- Presence of other associated symptoms for the last 24 hours: nausea, vomiting, abdominal pain, anal irritation.

One faecal sampling for microbiological examination will be collected as soon as possible after inclusion for microbiological laboratory testing (for virology, bacteriology and parasitology testing) in order to determine the microbiological status of this acute diarrhoea episode, i.e. the absence/presence of the following faecal pathogens:

Virology testing:

- Rotavirus,
- Adenovirus,
- Norovirus.

Bacteriology and parasitology testing:

- Enteropathogenic and Enterotoxigenic Escherichia Coli (E. coli),
- Staphylococcus aureus,
- Shigella,
- Salmonella,
- Campylobacter,
- Yersinia enterocolitica,
- Amoebiasis (entamoeba histolytica),
- Giardia / lamblia.

1.3.2.4 *Withdrawal/discontinuation*

In case of either:

- impaired general health condition
- and/or moderate or severe dehydration
- and/or fever above 38°C

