(f) Sensitivity analysis – recovered patients without recovery confirmation.

For patients whose last stool is a formed stool without any other subsequent stool to allow the confirmation of the recovery will be considered having recovered. This new endpoint will be analysed using the same methodology as for the primary efficacy endpoint on the ITT set.

(g) Baseline prognostic factors

The same subgroup analysis will be performed for the following baseline variables: Season of randomisation, Absence/Presence of faecal pathogens (virology, bacteriology and parasitology testing), Time since diarrhoea onset.

Cox analyses to assess the impact of baseline prognostic factors

A multivariate analysis of the time-to-recovery will be performed in order to take into account prognostic factors. A Cox proportional hazards model [2] will be performed to estimate the HR and its two-sided 95% CI.

The factors included in this analysis will include but will not be limited to (see section 3.2.18 for the parameterization):

Table 2 Prognostics factors for the Cox model analysis

Covariate	Categories
Time since diarrhoea onset	≤ median (reference) > median
Number of watery stools during the last 24 hours prior inclusion	Not applicable.
Country	Algeria, Czech Republic, Egypt, Lebanon, Poland, Tunisia (largest country to be used as reference)
Season of randomisation	Winter (reference), Summer.
Absence/presence of faecal pathogens for Virology testing	Positive (Rotavirus or Adenovirus or Norovirus) (reference), Negative (None) Not done/missing
Absence/presence of faecal pathogens for Bacteriology testing	Positive (Enteropathogenic or enterotoxigenic E. Coli or Staphylococcus aureus or Shigella or Salmonella or Campylobacter or Yersinia enterocolitica) (reference) Negative (None) Not done/missing
Absence/presence of faecal pathogens for Parasitology testing	Positive (aemibiasis or Giardia/lamblia) (reference), Negative (None) Not done/missing.

Since it is an exploratory search, other covariates may be added.

Step1:

Each of the potential factors associated with recovery listed in Table 2 together with the treatment variable will be tested in separate Cox proportional hazards models. Any factors found to be significant at $p \leq 0.20$ (via the Wald chi-square test statistic)

will be considered to be potentially important. The association between each covariate and treatment will be further explored by presenting separate KM plots for each level of the covariate.

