3.2.6.2 Other Baseline characteristics

- History of disease: diarrhoea episode characteristics will be summarized using the following information from the “History of current acute diarrhoea episode” eCRF page:
 - Duration since diarrhoea diagnosis (hours): summary statistics
 - Time since diarrhoea onset: number (%) in categories [0-12H]; [12-24H]; [24-36H]; [36-48H]; ≥48H.
 - Number of stools during the last 24 hours: summary statistics on overall and for:
 - Stools/unformed loose or watery stools of the first 12 hours-period
 - Stools/ unformed loose or watery stools of the second 12 hours-period
 - Presence of associated symptoms during the last 24 hours: number (%) of subjects in each category Nausea (Yes/No), Vomiting (Yes/No), Abdominal pain (Yes/No), Anal irritation (Yes/No).
- Results of virology/microbiology for stool examination:
 - Results of Virology testing with number (%) of subjects in each category: Rotavirus, Adenovirus, Norovirus, None, Missing.
 - Results of Bacteriology and parasitology testing with number (%) of subjects in each category:
 - Bacteriology subgroups: Enteropathogenic and enterotoxigenic E. Coli, Staphylococcus aureus, Shigella, Salmonella, Campylobacter, Yersinia enterocolitica, None, Missing.
 - Parasitology subgroups: Aemibiasis (entamoeba histolytica), Giardia/lamblia, None, Missing.
 - Additionally, above frequency tables will be provided with number (%) of patients with a positive result to:
 - Virology and parasitology,
 - Virology and bacteriology,
 - Parasitology and bacteriology,
 - Virology, bacteriology and parasitology.

3.2.7 *Medical and surgical history, Non-Drug therapies, concomitant surgical procedures*

Medical and surgical history will be coded using MedDRA Version 22.0 as well as Prior and Concomitant Non-Drug therapies and Concomitant Surgical Procedures.

Listings will present the preferred term and verbatim text. The listings will be sorted by treatment group, subject, primary system organ class, preferred term and verbatim text.

Frequency tables of the number and percentage of subjects will be provided by primary system organ class and preferred term for each treatment group for:

SAP Final Version: 15 July 2019

31/50

- Prior medical and surgical history: separately for prior and ongoing conditions
- Concomitant non-drug therapy
- Concomitant surgery.

Prior non-drug therapies will only be listed.

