Duration since current diarrhoea diagnosis (in hours) will be defined using the date/time of diarrhoea onset as recorded in the “History of current acute diarrhoea episode” eCRF page:

$$\text{Duration (hours)} = (\text{date/time of randomisation} - \text{date/time of diarrhoea onset}).$$

- **AE duration**

If the start and end dates of the AE are identical then “<1” day will be presented. If the duration is greater than 24 hours then it will be calculated as (end date - start date) +1 and presented in days. If the recorded end date is CONT. (for continuing), the end date will be listed as “ongoing” and the duration will be approximated as “ \geq (last attended visit date - start date)+1” day(s). If the start date or the end date are

partial the duration will be presented as a superior inequality “≥xx” day(s) (i.e., ≥2 where start date = 31 January 2004 and end date = February 2004 or start date = January 2004 and end date = 01 February 2004].

- **Time since last treatment intake for adverse event**

If the start date of the adverse event is identical to the date of last administration intake, then “<1” day will be presented. If the time to onset is greater than 24 hours then it will be calculated as (start date – last treatment intake date) +1 and presented in days.

If the start date is partial, the time since 1st treatment intake will be presented as a superior inequality (i.e., for an AE started in February 2004 after the last treatment intake performed on 31 January 2004, the time since last treatment intake will be as “≥2” days). If the start date is missing the time since last treatment intake will not be presented.

- **Concomitant therapy duration:**

The duration of concomitant treatments will be calculated as (end date – start date) + 1. If the recorded end date is CONT. (for continuing), the end date will be listed as “ongoing” and the duration will be approximated as “≥ (last attended visit date – start date)+1” day(s). If the start date or the end date are partial, the duration will be presented as an inequality “≥ xx” day(s) (i.e. ≥2 where start date=31JAN2004 and end date=FEB2004 or start date=JAN2004 and end date=01FEB2004) but if both are partial or one is missing, the duration will not be presented.

- **Medical and surgical history duration**

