3.2.18 Covariates and analysis of subgroups

Subgroups analyses on the primary endpoint are planned for the following group of variables:

Time since diarrhoea onset

- \leq median (reference)
- $>$ median

Country (largest country to be used as reference)

- Algeria
- Czech Republic,

SAP Final Version: 15 July 2019

39/50

- Poland,
- Tunisia
- Egypt
- Lebanon

Season of randomisation:

- Winter (reference)
- Summer

Virology subgroup:

- Positive (reference): at least Presence of one of the following:
 - (a) Adenovirus ,
 - (b) Rotavirus,
 - (c) Norovirus,
- Negative: no presence and at least one absence among all above tests
- Not done or missing result for all tests.

Bacteriology subgroup:

- Positive (reference): at least Presence of one of the following:
 - (a) Enteropathogenic or enterotoxigenic E. Coli
 - (b) Staphylococcus aureus,
 - (c) Shigella,
 - (d) Salmonella,
 - (e) Campylobacter,
 - (f) Yersinia enterocolitica,
- Negative: no presence and at least one absence among all above tests
- Not Done or missing result for all tests.

Parasitology subgroup:

- Positive (reference): at least Presence of one of the following:
 - (a) Aemibiasis (entamoeba histolytica)
 - (b) Giardia/lamblia
- Negative: no presence and at least one absence among all above tests
- Not done or missing result for all tests.

Covariables used in mixed models will be:

- Number of stools 24 hours before randomisation (baseline) as recorded in the “History of current acute diarrhoea episode” eCRF page and calculated as follows: Number of stools during the first 12-hour period + Number of stools during the second 12-hour period.
- Number of watery stools 24 hours before randomisation (baseline) calculated as follows: Number of watery stools during the first 12-hour period + Number of watery stools during the second 12-hour period.

Missing values will not be replaced.

4 COMPUTER SYSTEMS, SOFTWARE AND VALIDATION OF PROGRAMS**4.1 Hardware**

The statistical analysis will be performed using a computer on a Windows 7 operating system.

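### The exploratory Cox model enters time since diarrhoea onset only as a median split, although hours are available, which weakens its onset effect and its treatment-by-onset interaction test

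*SAP*

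**What the plan says.** **Collection.** Protocol section 5.2.1 asks at Visit 1 for the "date and time (hours, minutes) of first watery stool". SAP section 1.3.2.3 records the "Date and time (hours, minutes) of first unformed loose or watery stool". The inclusion criterion in Protocol section 4.1 limits the episode to one "having started within 48 hours before Visit 1 (first study drug intake time".

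**Derivation.** SAP section 3.2.12 already produces the variable on a continuous scale: "Duration since current diarrhoea diagnosis (in hours) will be defined using the date/time of diarrhoea onset", subtracted from the date and time of randomisation. Section 3.2.6.2 summarises these hours and also tabulates 12-hour bands ("Time since diarrhoea onset: number (%) in categories"), but only as baseline description.

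**Use in the model.** Table 2 lists the covariate with two levels, "≤ median (reference) > median", and refers to section 3.2.18 for the parameterisation. That section is introduced by "Subgroups analyses on the primary endpoint are planned for the following group of variables" and gives "Time since diarrhoea onset" the same two levels. In Table 2 the number of watery stools has no categories, so it appears to enter as a count. Step 2 of the selection procedure provides for continuous variables.

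**Status.** SAP section 3.1.4 makes only the primary ITT analysis of the primary endpoint confirmatory. Section 3.2.1.1 (g) describes the Cox work as exploratory and allows covariates to be added. The SAP gives no reason for the cut and no value for it in hours.

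**The concern.** A median split treats everyone on one side of the cut as identical, and people just either side of it as different. If the median were 24 h, subjects at 1 h and 23 h would share a level while subjects at 23 h and 25 h would not. The cut in hours is unknown until the data are in.

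This model is the SAP's planned look at how prognostic factors bear on recovery and on the treatment effect. Time since onset must pass a screen at p ≤ 0.20 and a stepwise selection (0.20 to enter, 0.15 to remove). Its interaction with treatment is then kept if p ≤ 0.10. Whether the treatment works differently when started early or late in the episode is a natural question here, and the split makes a graded answer harder to detect.

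**Working it through.** **The plan's own figure.** The documents state no figure for information lost by the split. The only related number is the sample size, and it reproduces. With medians of 55 h and 70 h the hazard ratio is 55/70 = 0.786. The Schoenfeld formula gives 540 events and Freedman's gives 546. Dividing by 0.75, the efficiency of the Gehan-Wilcoxon test relative to the log-rank test for uncensored exponential times, gives 720 and 728 against the stated 726. Then 726/0.85 = 854.1 against 854. Time since onset does not enter this calculation.

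**Information kept by the split.** For a small linear effect on the log hazard, the fraction kept is the squared correlation between X (hours since onset) and D (X above the median). Because treatment is randomised independently of X, the same fraction applies approximately to the treatment-by-onset interaction.

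- Uniform over 0-48 h: cov(X, D) = 0.5 × 36 − 24 × 0.5 = 6. SD(X) = 48/√12 = 13.86 and SD(D) = 0.5. Correlation = 6/(13.86 × 0.5) = 0.866, and its square is 0.75. Loss: 25%.
- Normal: correlation = 0.399/0.5 = 0.798, and its square is 2/π = 0.637. Loss: 36%.

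**Power.** Let δ be the standardised effect that gives 80% power with hours at two-sided 0.10: δ = 1.645 + 0.842 = 2.486 before rounding. With the split, power ≈ Φ(δ√r − 1.645), where r is the fraction kept.

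| Assumed shape of onset times | Kept (r) | δ√r | Power at 0.10 |
|---|---|---|---|
| Two separated clusters (12 h and 36 h, SD 4 h) | 0.90 | 2.359 | 76% |
| U-shaped, beta(0.5, 0.5) | 0.81 | 2.238 | 72% |
| Uniform 0-48 h | 0.75 | 2.153 | 69% |
| Beta(2, 2) | 0.702 | 2.083 | 67% |
| Normal | 0.637 | 1.984 | 63% |
| Exponential (mean 12 h) truncated at 48 h | 0.562 | 1.864 | 59% |

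The other shapes tried were triangular, truncated normal, truncated lognormal and a longer truncated exponential. They lost 31-35%.

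At the p ≤ 0.20 screen, δ = 1.282 + 0.842 = 2.123 before rounding. A covariate with 80% power in hours falls to Φ(2.123 × 0.866 − 1.282) = 71% if onset is uniform, and to Φ(2.123 × 0.798 − 1.282) = 66% if normal.

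**Simulation check.** Cox models were fitted to 854 simulated subjects with exponential times, medians of 55 h and 70 h, and an onset effect of 0.1 or 0.2 per SD. There were only 28-30 runs per setting, so the results are rough.

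- Ratio of (mean Wald chi-square − 1), split to continuous: 0.73 and 0.75 for uniform onset, 0.68 and 0.63 for normal onset.
- Treatment hazard ratio: changed by less than 0.2% (for example 1.273 with hours and 1.271 with the split). Its standard error was 0.073 both ways.
- Passing the p ≤ 0.20 screen: 93% both ways at 0.1 per SD, and 100% both ways at 0.2.

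**The case against.** The best case for leaving the SAP alone has four parts.

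- **Nothing confirmatory depends on it.** The primary test has no covariates described, and the Cox model is labelled exploratory. This stands and sets the weight of the point.
- **The treatment estimate is indifferent to the coding, and strong onset effects survive it.** The simulation supports both statements. In a further 300 simulated trials of 769 subjects at 0.2 per SD, the mean likelihood-ratio chi-squares were 21.9 (split) and 28.8 (hours), both far past every threshold in the procedure. The loss matters for weaker onset effects and for the interaction, where power is not already near 100%.
- **The size is assumed.** This also stands. The documents give neither the distribution nor the shape of the effect. If the true effect were a step near the median, the split would lose little or could do better. Onset is also recalled as history at Visit 1, so the recorded minute overstates its real precision. Section 3.2.6.2 allows a category of 48 h or more, and a linear term is sensitive to such values.
- **The procedure relies on levels.** Kaplan-Meier plots by level, hazard ratios within levels for a significant interaction, and stratification if proportional hazards fails all need categories. This is a reason to keep the split for those uses. It is not a reason to use it as the model term.

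A reader might infer that the trial's power or its adjusted treatment comparison suffers, or that a quarter of the sample is in effect discarded. The documents and the checks do not support this: the loss is confined to one covariate and its interaction. A reader might also take the data-dependent cut for a cut-point search. It is a fixed rule on a baseline variable and is not chosen on the outcome.

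**Conclusion.** The point holds as a minor improvement to an exploratory analysis. Under a log-linear effect, the median split loses about 25% of the onset covariate's own information if onset is uniform over 0-48 h and about 36% if it is normal. Other shapes tried within 0-48 h ranged from 19% to 44%, and two well-separated clusters lost about 10%. An interaction test with 80% power in hours would have about 69% (uniform) or 63% (normal) at the 0.10 threshold.

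These figures rest on assumed distributions, linearity and a normal approximation, so no single percentage should be quoted without its condition. The primary result, the sample size and the stated power are untouched, and the adjusted treatment hazard ratio is practically the same either way.

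**What to change.** In SAP Table 2 and section 3.2.18, enter time since onset in hours as a continuous term for both the main effect and the treatment interaction. Use a linear term with a spline check for non-linearity, stating the knots and the decision rule in advance.

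Keep the median split for the subgroup table, the Kaplan-Meier plots, the forest plot, and any stratification needed if proportional hazards fails. If the treatment-by-onset interaction is retained, report the treatment hazard ratio at onset times stated in advance, in place of one ratio per level.

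No new data are needed and the confirmatory analysis does not change. The cost is the linearity check, the matching edit to section 3.2.18, and consequential wording where section 3.2.1.1 (g) assumes covariate levels: the plots, the within-level hazard ratios and the handling of non-proportional hazards.
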